R61 Power Analysis: We have conducted several power calculations in our previously published work used to determine the sample sizes proposed here. First, we have consistently found that an *n* of 14-16 healthy controls and an *n* of 14-16 PTSD patients provide adequate power to observe: 1) SCR differences and AMYG, vmPFC, HPC signal differences between groups during fear extinction and/or extinction recall; and 2) THC's effects on ETI and AMYG, vmPFC, and HPC activation in healthy controls. Similarly, normalization of corticolimbic responsivity to affective stimuli has been observed following exposure-based therapy in an *n* of 14 anxious patients¹⁴⁸ and following administration of a serotonin selective reuptake inhibitor (SSRI) with an *n* of 21 anxious patients¹⁴⁹. Given that the effect sizes tested within- and between-groups in previous fMRI studies have ranged between moderate to large (Cohen *d* = 0.7 - 1.5) with the anticipated cohort of 20 participants per group (PTSD-5mg, PTSD-10mg, PTSD-PBO, TEC), who complete the entire protocol with usable fMRI and SCR data, will confer >80% power to detect an effect size 0.72 or higher after necessary multiplicity adjustment.

PROTECTION OF HUMAN PARTICIPANTS

This Human Participants Research meets the definition of a clinical trial.

1. Risks to Human Participants

a. Human Participants Involvement, Characteristics, and Design

Involvement of Human Participants:

The total time commitment estimated per participant is 8.5-13 hr across all study visits. This is broken down below:

Visit 1: Screening & Study Entry: Approximately 3 hours for participants, unless a participant has already completed any of the screening assessments as part of another separate study. In this case, if the overlapping screening assessments were completed no more than 1 month prior to Visit 1 and the participant has signed HIPPA Authorization allowing us to access this prior data, Visit 1 will be approximately 1.5 hr.

Note: Due to the length and rigor of this initial screening process, it may sometimes be necessary for participants to complete screening measures across more than one visit (e.g., schedule conflicts). All screening measures will be completed within 2 weeks of the consent date.

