Visit 2: Fear Acquisition: Approximately 1 hr for all participants. Participants are considered enrolled in the study once they have begun Visit 2 (if enrolled in PTSD group, participant will be randomized). Visit 2 will occur within 6 months of Visit 1. If more than 6 months have passed, we will re-do Visit 1 before the participant is able to complete visits 2 – 5.

Visit 3: Fear Extinction: Approximately 5 hr for those receiving a capsule (PTSD groups) or approximately 3 hours for those not receiving a capsule (TEC group)

Visit 4: Fear Extinction Recall and Fear Renewal Test (approximately 24 hr after extinction, but no more than 1 week later): Approximately 1.5 hr

Visit 5: Fear Extinction Recall, Fear Renewal Test, & Debriefing (approximately 1 week after extinction, but no more than 3 weeks later): Approximately 1.5 hr

Nature of Participant Population: Participants of both genders will be included in the study and the age range of participants will be from 18-60. Persons below 18 or above 60 are excluded because beyond this range age may influence response to the drugs. Furthermore, the relatively small age range is intended to reduce variation in performance on the behavioral task. There are no enrollment restrictions based upon race or ethnic origin. Candidates will undergo a structured clinical psychiatric interview¹⁵⁰ and complete questionnaires related to their general physical health, current medications, with a detailed section on current and lifetime drug and alcohol use. This study will not involve vulnerable populations.

The number of participants expected to participate is 104: 78 trauma-exposed participants with PTSD and 26 trauma-exposed participants without PTSD (TEC; demographically matched). There will be 3 experimental groups: PTSD participants will be assigned to 5mg of THC (n=26), 10mg of THC (n=26), or a placebo (PBO) (n=26). The 26 TEC participants will not receive THC or PBO. With the conservative anticipation 25% will fail to complete all parts of the study, we estimate 20 PTSD participants in each condition (60 PTSD participants in total) and 20 TEC participants will complete the study for a total of 80 participants. Participants will be recruited from the Detroit community and mental health clinics. We will enroll up to 175 participants to guarantee enough viable data and to account for participant drop out.

Recruitment

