Weekly meetings of the research staff of this study will be conducted that will include review of accrual, consenting procedures, protocol adherence, AEs, and quality control of all data obtained from the study in the previous weeks. Minutes of these meetings will be recorded, signed by the PI, and archived in a Regulatory Folder on the lab server. In addition, to participant-specific protocol deviation forms, protocol deviation will also be documented in a study-wide deviations log to facilitate monitoring and reporting to regulatory authorities. Similarly, AEs will be also documented in a study-wide AE log, which will be used to facilitate safety monitoring and identify AE trends across subjects, as well as overall AE reporting to the IRB and NIMH.

We will conduct a preliminary analysis during the early stages of data collection (once \approx 10% of the THC group has completed the study) to assess the efficacy and safety of the 5mg and 10mg doses and submit an amendment to adjust the dosing as needed (e.g. if 10mg shows significant improvement over 5mg, a further

increase in dosing [15mg] would be worthwhile). Our efficacy and safety metrics are based on the following criteria:

- 1) a. At least a medium effect size (Cohen's $d \geq 0.05$) between THC and PBO conditions in BOLD responses in *a priori* ROIs (vmPFC and/or HPC) and/or peripheral measures (SCR, US expectancy, SUDS) during recall of extinction learning; or
 - b. Relationship between change in BOLD responses in *a priori* ROIs (vmPFC and/or HPC) and/or change in peripheral measures (SCR, US expectancy, SUDS) during recall of extinction learning in THC (vs. PBO) is of at least a medium effect size ($r \geq 0.30$).
- 2) There will be no adverse events of more than mild severity that are rated as possibly, probably, or definitely related to acute administration of THC (more than PBO) in PTSD participants.

We will apply O'Brien-Fleming¹⁷⁹ type monitoring bounds as guidelines for the decisions regarding continuation or early termination of the trial. In addition to efficacy comparisons, frequency of AEs along with formal statistical comparisons of the frequency of AEs will be performed.

Reporting responsibility

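### Interim efficacy criterion 1a labels Cohen's d ≥ 0.05 a medium effect; the number contradicts the label

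*Combined protocol and SAP*

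**What the plan says.** Section 5, Data and Safety Monitoring Plan, describes a preliminary analysis once about "10% of the THC group has completed the study". Its purpose is to assess the efficacy and safety of the two THC doses and, if needed, to submit an amendment on dosing. The criteria are introduced with "Our efficacy and safety metrics are based on the following criteria".

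- Criterion 1a reads "At least a medium effect size (Cohen's $d \geq 0.05$) between THC and PBO conditions". It applies to BOLD response in vmPFC and/or HPC, and/or to the peripheral measures (SCR, US expectancy, SUDS), during recall of extinction learning. It states no direction.
- Criterion 1b, joined to 1a by *or*, concerns a relationship between changes in these measures. It attaches the same medium label to a correlation of at least 0.30.

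The same section separately names O'Brien-Fleming "type monitoring bounds as guidelines for the decisions regarding continuation or early termination of the trial".

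The only other place that puts words to values of Cohen's d is the R61 Power Analysis, where effect sizes in previous fMRI studies "have ranged between moderate to large (Cohen *d* = 0.7 - 1.5").

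**The concern.** A threshold of 0.05 standard deviations cannot reasonably be called medium, and nothing in the documents supports that reading. A prespecified criterion should have one meaning. Here a reader may apply the number, apply the word, or choose between them after seeing the data.

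Criterion 1a is a named efficacy metric for the dosing review, and because of the *or* it can satisfy the efficacy part without 1b. Taken literally, it removes almost all of the efficacy hurdle: meeting it would say next to nothing about whether THC has a medium effect.

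**Working it through.** The threshold is stated without a derivation, so there is no calculation in the plan to reproduce. It can be checked against the documents' other figures and for how it behaves at the planned look.

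**1. Against criterion 1b.** With equal groups, r = d / √(d² + 4). For d = 0.05: 0.05 / √(0.0025 + 4) = 0.025. That is about one-twelfth of 0.30 (0.30 / 0.025 = 12). In the other direction, d = r / √((1 − r²) × 0.25), so r = 0.30 gives 0.30 / √(0.91 × 0.25) = 0.63. Criterion 1b measures something different from 1a, so the two thresholds need not be equal. The comparison shows only that one label is attached to very different magnitudes.

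**2. Against the R61 Power Analysis.** The lower end of the range called moderate to large is d = 0.7, and 0.7 / 0.05 = 14. That section does not define medium, but it gives no room for 0.05.

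**3. Chance of meeting 1a with no true effect.**

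Inputs:
- THC participants randomized: 26 + 26 = 52; expected to complete: 20 + 20 = 40 (Nature of Participant Population).
- THC completers at the look: 0.10 × 52 = 5.2, taken as 5; or 0.10 × 40 = 4.
- Placebo completers at the look: not given; assumed 2 to 5.
- Also assumed: the two THC doses pooled, one measure, normal data with equal variances.

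Formula: P(observed d ≥ c) = P(t > c × √(n₁n₂/(n₁+n₂))), with n₁ + n₂ − 2 degrees of freedom.

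Worked case, 5 THC and 3 placebo: √(15/8) = 1.369, with 6 degrees of freedom. For c = 0.05, t = 0.068 and P = 0.474. For c = 0.50, t = 0.685 and P = 0.260.

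| THC | Placebo | P(d ≥ 0.05) | P(d ≥ 0.50) |
|---|---|---|---|
| 5 | 2 | 0.477 | 0.288 |
| 5 | 3 | 0.474 | 0.260 |
| 5 | 4 | 0.471 | 0.240 |
| 5 | 5 | 0.469 | 0.226 |
| 4 | 2 | 0.478 | 0.297 |
| 4 | 3 | 0.475 | 0.271 |
| 4 | 4 | 0.473 | 0.253 |
| 4 | 5 | 0.471 | 0.240 |

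A simulation of 400,000 null trials with pooled-SD d agrees: 0.473 and 0.259 at 5 versus 3, and 0.479 and 0.297 at 4 versus 2.

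The table requires a favourable direction, which 1a does not print. If a difference in either direction counts, each value doubles: 0.94 to 0.96 at 0.05, and 0.45 to 0.59 at 0.50.

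These are probabilities that one measure meets the criterion, not decision error rates. The *and/or* across measures raises the chance that at least one meets it, by an amount that depends on correlations the documents do not give.

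**The case against.** The best counter-argument is that this is an evident misprint, that the word *medium* carries the intent, and that nothing shows the team would apply 0.05 literally. Four further points support it.

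- **The value 0.50 is not in the documents.** It is a convention. It also lies below the 0.7 at which the power section's moderate-to-large range starts, and below the 0.63 equivalent to r = 0.30. This stands: the sponsor has to supply the figure.
- **Correcting the number rescues little.** At 0.50 a single null measure still passes with probability 0.23 to 0.30. If the five named measures were independent, which is only an illustration, the chance that at least one passes at 5 versus 3 would be 1 − (1 − 0.474)⁵ = 0.96 at 0.05 and 1 − (1 − 0.260)⁵ = 0.78 at 0.50; positive correlation would lower both. This also stands. The smallness of the look and the number of alternative measures are a separate weakness.
- **The link to action is loose.** No rule ties 1a to a decision, the plan's dosing example compares the two doses with each other, a dosing change needs an amendment, and continuation is referred to the O'Brien-Fleming bounds. This limits the consequence. But 1a is still a stated efficacy metric for that review, and the plan does not say that the bounds replace it.
- **The text was machine-read.** A misread digit cannot be excluded, though nothing points to one. The sponsor's confirmation would settle it.

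None of this reconciles the number with its label. An obvious slip in a prespecified threshold still needs correcting, because the documents themselves do not tell the reader which of the two governs.

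**Conclusion.** The concern holds. The label and the number in criterion 1a are incompatible, and the documents' own figures show it without any outside source. The size of the problem, for one null measure with favourable direction required and the completer numbers assumed above, is a pass probability of 0.47 to 0.48 as printed, compared with 0.23 to 0.30 if 0.50 was meant.

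Confidence in the contradiction is high. That 0.50 was the intended value is probable but not documented. The finding does not show that 1a governs stopping, and it does not imply that a corrected threshold would make the preliminary analysis reliable. It should be fixed, because a named metric for the dosing review currently sets almost no efficacy hurdle.

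**What to change.** The sponsor should confirm the intended threshold and correct criterion 1a so that the number agrees with the word *medium* (conventionally d ≥ 0.50). If another value was intended, it should be stated together with the label that fits it.

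The cost is one number in the monitoring plan. The timing of the look, the sample size and the data collected do not change. No dose or dosing rule is proposed here.
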